2.4. Expectations and role to the project

From the observational and the interventional phases of the study, novel outcomes are expected to occur, of interest for both the NUTRISHIELD project as well as the scientific community.

The proposed study incorporates knowledge produced under NUTRISHIELD, as materials and methods designed under WP3 - 6 and WP9 that will be directly applied within its context. Findings from the observational phase are expected to highlight novel associations between several, not yet adequately studied, biomarkers and pediatric obesity/ diabetes progression. It will also underscore the most valid means of dietary assessment for this population, and the knowledge produced shall be directly applied to the interventional phase of the study.

[figure not shown]
Another major expected outcome of this study is the validation of the NUTRISHIELD project in clinical settings during the intervention phase, in essence describing how a theoretical framework designed and fed by the patients' data translates to clinical practice.

2.6. Study I CONSORT 2010 checklist

Table 2.2: Study I CONSORT 1

	Item		Reported on
Section/Topic	No	Checklist item	page No
Title and abstract			
	1a	Identification as a randomised trial in the title	Non-applicable
	1b	Structured summary of trial design, methods, results, and conclusions (for specific guidance see CONSORT for abstracts)	Non-applicable
Introduction			
Background and	2a	Scientific background and explanation of rationale	7-8
objectives	2b	Specific objectives or hypotheses	8
Methods			
Trial design	3a	Description of trial design (such as parallel, factorial) including allocation ratio	8
	3b	Important changes to methods after trial commencement (such as eligibility criteria), with reasons	Non-applicable
Participants	4a	Eligibility criteria for participants	10
	4b	Settings and locations where the data were collected	10
Interventions	5	The interventions for each group with sufficient details to allow replication, including how and when they were actually administered	14-15
Outcomes	6a	Completely defined pre-specified primary and secondary outcome measures, including how and when they were assessed	16-19
	6b	Any changes to trial outcomes after the trial commenced, with reasons	Non-applicable
Sample size	7a	How sample size was determined	18-19
	7b	When applicable, explanation of any interim analyses and stopping guidelines	Non-applicable
Randomisation:			
Sequence	8a	Method used to generate the random allocation sequence	19
generation	8b	Type of randomisation; details of any restriction (such as blocking and block size)	19

This document is part of a project that has received funding from the European Union's Horizon 2020 research and innovation programme under grant agreement No 818110. It is the property of the NUTRISHIELD consortium and shall not be distributed or reproduced without the formal approval of the NUTRISHIELD Management Committee. The content of this report reflects only the authors' view. EC is not responsible for any use that may be made of the information it contains.

Allocation concealment mechanism	9	Mechanism used to implement the random allocation sequence (such as sequentially numbered containers), describing any steps taken to conceal the sequence until interventions were assigned	19
Implementation	10	Who generated the random allocation sequence, who enrolled participants, and who assigned participants to interventions	19
Blinding	11a	If done, who was blinded after assignment to interventions (for example, participants, care providers, those assessing outcomes) and how	19
	11b	If relevant, description of the similarity of interventions	Non-applicable
Statistical methods	12a	Statistical methods used to compare groups for primary and secondary outcomes	19-20
	12b	Methods for additional analyses, such as subgroup analyses and adjusted analyses	Non-applicable
Results			
Participant flow (a diagram is strongly	13a	For each group, the numbers of participants who were randomly assigned, received intended treatment, and were analysed for the primary outcome	Non-applicable
recommended)	13b	For each group, losses and exclusions after randomisation, together with reasons	Non-applicable
Recruitment	14a	Dates defining the periods of recruitment and follow-up	Non-applicable
	14b	Why the trial ended or was stopped	Non-applicable
Baseline data	15	A table showing baseline demographic and clinical characteristics for each group	Non-applicable
Numbers analysed	16	For each group, number of participants (denominator) included in each analysis and whether the analysis was by original assigned groups	Non-applicable
Outcomes and estimation	17a	For each primary and secondary outcome, results for each group, and the estimated effect size and its precision (such as 95% confidence interval)	Non-applicable
	17b	For binary outcomes, presentation of both absolute and relative effect sizes is recommended	Non-applicable
Ancillary analyses	18	Results of any other analyses performed, including subgroup analyses and adjusted analyses, distinguishing prespecified from exploratory	Non-applicable
Harms	19	All important harms or unintended effects in each group (for specific guidance see CONSORT for harms)	Non-applicable
Discussion			
Limitations	20	Trial limitations, addressing sources of potential bias, imprecision, and, if relevant, multiplicity of analyses	Non-applicable
Generalisability	21	Generalisability (external validity, applicability) of the trial findings	Non-applicable
Interpretation	22	Interpretation consistent with results, balancing benefits and harms, and considering other relevant evidence	Non-applicable
Other information			

D2.7 – Clinical protocols for clinical studies

Draft, V1.2 – 28/06/2019 H2020 Contract No 818110

Registration	23	Registration number and name of trial registry	Non-applicable_
Protocol	24	Where the full trial protocol can be accessed, if available	Non-applicable
Funding	25	Sources of funding and other support (such as supply of drugs), role of funders	Non-applicable

Project Acronym: Nutrishield

Grant Agreement number: 818110 (H2020-SFS-2018-IA)

Project Full Title: Fact-based personalised nutrition for the young

3. Study II protocol: Personalised nutrition for lactating mothers

3.1. Background

Breastfeeding is the optimal feeding practice for all infants, associated with numerous health benefits for the mother—infant dyad, being an ecologic practice as well [1]. The World Health Organization highly recommends exclusive BF for all infants up to 6 months, born either full—term [2, 3] or prematurely [4]. Human Milk (HM) is a dynamic fluid that meets offspring's needs [5-8], and is ample in nutrients and bio-active compounds intended to enhance the offspring's immunity and growth [9]. HM also hosts a complex ecosystem of microbiota [10], which is of paramount importance for the offspring's immunity [5].

During the last decades, the incidence of preterm deliveries (<37 weeks of gestation) has been steadily increasing, and so has the interest in pre-term and early infant nutrition. Associated birth complications are the leading cause of death among children under 5 years of age, responsible for ~1 million deaths per year [11]. Progress in medical interventions has allowed for enhancing survival of an increasing proportion of extremely low gestational age newborns and low birth weight infants. Early infant nutrition has become a major player in improving clinical outcomes of survivors [12]. HM is recommended for preterm infants based on an impressive array of benefits provided to this highly vulnerable population, including ameliorated immunological and gastrointestinal outcomes [13-19].

For mothers unable to produce sufficient milk quantities so as to exclusively or partially breastfeed, pasteurized donor human milk (DHM) is a viable option to avoid formula feeding, especially for low birth-weight children [20]. To date most studies focus on the benefits of using DHM over formula in preterm infants, when own mother's milk (OMM) is limited or unavailable. There is clear scientific evidence indicating the superiority of OMM or DHM against formula feeding [21]. In relation to DHM, its use over infant formula protects against necrotizing enterocolitis [22]; but there are few reports comparing DHM and OMM. While DHM provides some bioactive agents, its consumption is associated with slower growth rates in comparison with the consumption of OMM or formula, although inconclusively [21]. This

This document is part of a project that has received funding from the European Union's Horizon 2020 research and innovation programme under grant agreement No 818110. It is the property of the NUTRISHIELD consortium and shall not be distributed or reproduced without the formal approval of the NUTRISHIELD Management Committee. The content of this report reflects only the authors' view. EC is not responsible for any use that may be made of the information it contains.

finding may be attributable to several factors. Most DHM is provided by women who have delivered at term and donate their milk in later stages of lactation several months after delivery. In comparison to preterm milk during the first weeks after delivery, this milk is low in protein, fat and other bioactive molecules [23]. Its composition is also affected by the processing of expressed milk, including stringent protocols applied in human milk banks, i.e. pasteurization, freezing, and storage (25, 26), necessary to circumvent the potential risk of transmitting infectious agents.

Beyond the physiological adaptations of HM composition, research has focused on the potential effects of the maternal diet on the HM composition. In an earlier report, HM's composition was found rather constant among mothers of diverse ethnic backgrounds, with different dietary habits [24]. The total fat content of HM has been found to be independent of the mother's diet [25], but responsive to the mother's fatty acids dietary intake [26, 27]. In a recent comprehensive systematic review of 104 observational and interventional studies, HM composition was found to relate to the maternal consumption of fatty acids, fat-soluble vitamins, vitamin B1 and vitamin C intakes [28, 29]. No similar relationships were found for dietary intake of iron, folate, calcium, selenium or proteins [28]. However, more studies are needed to conclude for other nutrients and little is known on how the maternal diet may also affect non-nutritive constituents of the HM, i.e. prebiotics content[30], interactions with gut microbiota [31, 32]. Finally, existing evidence is mainly based on studies on full-term infants; the impact of maternal nutrition on the composition of the HM for the pre-term offspring has not been adequately documented. Thus, it still remains unknown whether dietary advice to the nursing mother could enhance the premature offspring's growth rate, and if so, whether non-nutritive aspects of the HM play any part, or mediate this process.

3.2. Objectives

The objectives of the study are:

- a) to evaluate associations between the mother's diet composition and HM composition in pre- and full-term infants, i.e. how the potential associations between mother's diet and HM nutrient composition is affected by prematurity.
- b) to evaluate the effect of pasteurization/storage on DHM composition.

c) to evaluate associations between HM composition (OMM or DHM) on growth and other health parameters in pre- and full-term infants.

3.3. Methods

Overall study design, participants, study phases (baseline, observational), sampling and statistical analysis are described in the following sections.

3.3.1. Study design

The proposed study is an observational, parallel group, non-randomized study in lactating mothers. It will be carried out at the University and Polytechnic Hospital La Fe (HULAFE), beginning at Month 21. Previously, the study protocol will be approved by the Ethics Committee for Biomedical Research of the Health Research Institute La Fe (Valencia, Spain) and the study participants will sign a relevant consent form. All procedures regarding volunteers' recruitment and participation, data security and handling will be in absolute accordance with the principles set under WP 9, concerning Ethical Requirements, and more specifically stated on Tasks 7.1 and 7.2 and D 7.2.

To address the objectives mentioned above, three mother-infant groups will be examined. In specific:

- Group A will consist of 25 pre-term infants fed with OMM (PT-OMM) and their mothers.
- Group B will consist of 25 pre-term infants fed with pasteurized DHM (PT-DHM), in range of complete enteral nutrition (150 mL/kg/day), and their mothers.
- Group C will consist of 25 full term infants receiving OMM (FT-OMM) and their mothers.

The study will be divided into two phases:

- A baseline phase, referring to the period between the time of delivery and the time preterm infants receive complete enteral nutrition (CEN) and full term infants recover of birth weight (RBW). During this period, all infants and their mothers will be evaluated, as described in the next section.
- 2. **An observational phase**, lasting six months and referring to the period that infants are fed with HMand/or formulas orsolid foods. During this period, assessments, as described below,

[figure not shown]

will be arranged for all mother-infants dyad and the donors providing the DHM in the hospital or the participants' home.

3.3.1.1. Schematic study design

The study design and comparisons among groups to address the objectives of the study are presented schematically in Figures 3.1 and 3.2 below.

Figure 3.1: Study II design

[figure not shown]

Every point represents the time points where assessments are to be made

CEN: complete enteral nutrition, RBW: recovery of birth weight

Figure 3.2: Group comparisons in relation to the study objectives

Obj. a: objective a. Obj. b: objective b. Obj. c: objective c

[figure not shown]
3.3.2. Participants

Participants will be recruited in HULAFE. Visits at baseline, when preterm infants receive complete enteral nutrition (CEN; i.e. 150 mL/kg/day) and at months 1, 3, and 6 will be held at the hospital. Visits when full term infants recover of birth weight and at month 2 will be held at the participant's home.

The eligibility criteria for participating will be as follows:

Inclusion criteria

- Mother accepts to participate in the study and signs an informed consent form
- Gestational age < 32 weeks for the group of preterm infants and gestational age > 37 weeks for the full-term infants
- Exclusive consumption (i.e. >80% of intake) of OMM or DHM

Exclusion criteria:

- Mother requires special diet (e.g. celiac disease, diabetes)
- Mother consuming probiotics
- Infant needs intestinal surgery
- Severe congenital malformations
- Chromosomopathies

3.3.3. Baseline Study Phase

At the baseline, sociodemographic and medical history information will be recorded and lifestyle, dietary, anthropometric, genotype, metabolome and microtype assessments will be performed as described below. Detailed Standard Operating Procedures employed for sample collection, storage and outcome assessment will be provided in WP3. Results obtained from data analysis will be used to feed the NUTRISHIELD platform and train the NUTRISHIELD algorithm, to be used as an asset for future reference.

3.3.3.1. Measurements

During their stay at the hospital mothers of all three groups will receive nutritional advice based on current knowledge and following the standard protocols of HULAFE.

Measurements concern sociodemographic information, dietary and other lifestyle behaviors, anthropometry, medical history, genotype, metabolome, and microbiome.

Sociodemographic information

Mothers of PT-OMM, PT-DHM and FT-OMM and donors providing the DHM will be asked to self-characterize their annual household income and their family income (ranging from 1, 0-4,999 € to 9, over 50,000 €), whether they have active health insurance (yes/no), their employment status (1, unemployed; 2, employee in private sector; employee in public sector; 3, self-employed; 4, working without pay in family business; 5, on leave (excluding maternity); 6, pensioner), whether they are on maternity leave (yes/no) and their marital status (1; married, 2; unmarried/co-habiting, 3; single parent, 4; divorced or separated, 5; widowed) [33, 34]. Education level will be described by the number of years

H2020 Contract No 818110

on education, while information about the number of people living with the family and in the household will also be included. Maternal or donor's age and origin will be recorded (1; White, non-Hispanic; 2; Black, non-Hispanic; 3, Hispanic; 4, Asian; 5, other).

Dietary assessment

Mothers of PT-OMM, PT-DHM, and FT-OMM will complete a validated semi-quantitative food frequency questionnaire (FFQ) [35]. FFQ will be administered by trained personnel and it comprises 69 questions on the consumption of foods that are commonly eaten by various populations throughout a year, including dairy products, cereals, fruits, vegetables, meat, fish, legumes, added fats, alcoholic beverages, stimulants and sweets. Using a 6-grade scale ("never/rarely", "1-3 times/month", "1-2 times/week", "3-6 times/week", "1 times/day", "≥2 times/day"), participants will be required to indicate the absolute frequency of consuming a certain amount of food, expressed in g, milliliters or in other common measures, such as slice, tablespoon or cup, depending on the food. The previous month will be set as the timeframe.

According to the FFQ responses, adherence to the Mediterranean Diet will be evaluated by using the MedDietScore, an 11-item composite score calculated for each participant from the FFQ-based food consumption [36]. For food groups presumed to be part of the Mediterranean pattern (i.e. those with a recommended intake of 4 servings per week or more, such as non-refined cereals, fruits, vegetables, legumes, olive oil, fish, and potatoes) higher scores will be assigned when the consumption is according to the rationale of the Mediterranean pattern, while lower scores will be assigned when participants report no, rare, or moderate consumption. For the consumption of foods presumed not to be part of the Mediterranean pattern (i.e. consumption of meat and meat products, poultry, and full fat dairy products), scores will be assigned on a reverse scale. For alcohol intake, a score of 5 was assigned for consumption of less than 300 ml of wine/day, a score of 0 was assigned for no consumption or for consumption of 700 ml/day and scores of 4 to 1 were assigned for consumption of 600-700, 500-600, 400-500 and 300-400 mL/day, respectively. All alcoholic beverages will be converted into ml of wine, assuming that 12 g of ethanol correspond to 100 mL of wine. The theoretical range of the MedDietScore is between 0 and 55. Higher values of the score indicate greater adherence to the Mediterranean diet.

H2020 Contract No 818110

Other lifestyle behaviors assessment

Physical activity levels of mothers of PT-OMM, FT-OMM and PT-DHM will be evaluated using the validated short version of the International Physical Activity Questionnaire (IPAQ) [37]. They will report the time spent on vigorous, moderate activities, walking (days/week, minutes/day) and sitting (hours/day) and their mean nocturnal sleep duration (in hours/day). All questions regarding sedentary and physical activity behavior refer to the last week, except for sleep, which refers to the last month.

Furthermore, the mothers will be asked regarding their smoking habits [38]. In specific current smoking status (yes/no), smoking frequency (1, daily; 2, less than daily; 3, not at all), smoking during pregnancy (yes/no), past smoking (yes/no), exposure to second hand smoking (yes/no), exposure to second hand smoking during pregnancy (yes/no), age of daily smoking initiation and the date of smoking cessation will be recorded.

o Anthropometric assessment

Weight and height of mothers of the PT-OMM, PT-DHM, and FT-OMM will be measured. Weight will be measured on a levelled platform scale to the nearest 0.5 kg and height on wall-mounted stadiometer, to the nearest 0.5 cm. Body Mass Index (BMI) (kg/m²) will be calculated by dividing the weight in kilograms by the height in meters squared.

All infants will be evaluated regarding their growth by measuring weight, length and cranial perimeter upon every visit at the hospital. Weight and recumbent length will be measured on an electronic baby scale and on a neonatometer scale, to the nearest 0.5 kg and 0.5 cm respectively and cranial perimeter will be measured using a flexible inch tape to the nearest 0.5 cm.

Medical history assessment

At observational phase PT-OMM, PT-DHM and FT-OMM mothers' medical history, i.e. all the chronic conditions that they may have as well as the use of medicines, will be recorded.

Genotype characterisation

A buccal swap sample will be collected from mothers of PT-OMM, PT-DHM and FT-OMM at baseline. In specific, standard buccal swab kits will be used to gather DNA sample. Furthermore, umbilical cord

blood will be extracted from PT-OMM, PT-DHM, and FT-OMM newborns. The detailed protocol is described in Deliverable 3.1.

Metabolomecharacterisation

For the characterization of metabolic profile urine samples will be collected from mothers of PT-OMM, PT-DHM and FT-OMM and their infants, as described in Deliverables 2.2 and 3.1.

Microbiome assessment

Fecal samples from all mothers and their infants will be collected for studying the microbiome. The protocol followed is described in Deliverable 2.1.

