3.3.4.1. Measurements

Measurements concern sociodemographic information, dietary and other lifestyle behaviors, anthropometry, medical history, genotype, metabolome, and microbiome.

Dietary assessment

Upon every visit of the observational phase mothers of PT-OMM, PT-DHM, and FT-OMM as well as donors providing the DHM will complete a validated semi-quantitative food frequency questionnaire (FFQ) [35], from which MedDietScore, will be calculated [36], as described in section 3.3.3.

In addition, during the hospital visit at month 1 all mothers will be asked to return a 4-day food record, in which they will have recorded all foods and drinks consumed for three consecutive weekdays and one day of the weekend. Nutrients' intake will be calculated using the Nutritionist Pro™ Diet Analysis (Axxya Systems, Woodinville, WA, USA) software. The research team involved in the diet analysis is competent in using the proposed software, and HUA has a long history of analyzing dietary data through it. Another strength of the proposed software is that it comprises food databases from multiple countries, which can be used to extrapolate the most relevant and reliable reference. We aim to cross-match intake data, and compare the validity of the FFQ against the 4-day food record, in order for the most valid to be used in the platform.

Other lifestyle behaviors assessment

Physical activity levels of mothers of PT-OMM, FT-OMM and PT-OMM as well as milk donors providing DHM will be evaluated at every visit, as described in section 3.3.3.

Furthermore, the mothers will be asked regarding their smoking habits [38]. In specific current smoking status (yes/no), smoking frequency (1, daily; 2, less than daily; 3, not at all) and exposure to second hand smoking (yes/no) will be recorded.

[figure not shown]
Anthropometric assessment

Weight and height of mothers of the PT-OMM, PT-DHM, and FT-OMM, as well as milk donors providing DHM will be measured and recorded at every visit at the hospital, as described above.

All infants will be evaluated regarding their growth by measuring weight, length and cranial perimeter upon every visit at the hospital. Weight and recumbent length will be measured on an electronic baby scale and on a neonatometer scale, to the nearest 0.5 kg and 0.5 cm respectively and cranial perimeter will be measured using a flexible inch tape to the nearest 0.5 cm.

Medical history assessment

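### Study II: the middle bands of the MedDietScore alcohol item are scored in reverse, so points rise with intake between 300 and 700 mL of wine a day

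*Protocol*

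**What the plan says.** Section 3.3.3.1 of the Protocol describes the MedDietScore as "an 11-item composite score calculated for each participant from the FFQ-based food consumption". It adds that "The theoretical range of the MedDietScore is between 0 and 55" and that "Higher values of the score indicate greater adherence to the Mediterranean diet".

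The alcohol item has three parts:

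- at the top, "a score of 5 was assigned for consumption of less than 300 ml of wine/day";
- at the bottom, "a score of 0 was assigned for no consumption or for consumption of 700 ml/day";
- in between, "scores of 4 to 1 were assigned for consumption of 600-700, 500-600, 400-500 and 300-400 mL/day, respectively".

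Other drinks are converted to wine, "assuming that 12 g of ethanol correspond to 100 mL of wine". Section 3.3.4.1 extends the score to every visit of the observational phase and to the milk donors: the mothers "as well as donors providing the DHM will complete a validated semi-quantitative food frequency questionnaire (FFQ", from which the MedDietScore is calculated as in section 3.3.3. No other part of the Protocol restates or corrects the item.

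**The concern.** The end points and the middle bands point in opposite directions. Going from 5 points below 300 mL/day to 0 at 700 mL/day makes sense only if points fall as intake rises. The four bands between them make points rise with intake. On a score where higher means closer adherence, a mother drinking 600-700 mL/day would then be rated better on this item than one drinking 300-400 mL/day.

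This is not a detail that a protocol would normally leave to a statistical analysis plan. The Protocol fixes the scoring rule, and this sentence is the only definition of the item in the document. A programmer who follows it literally will produce wrong item scores in all four bands. Study II results are also meant to feed the platform and train its algorithm, so a mis-scored variable could be carried beyond this study.

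**Working it through.** **Inputs.** All come from Protocol section 3.3.3.1: 5 points below 300 mL/day; 0 points at 700 mL/day; 0 points for no consumption; scores 4, 3, 2, 1 listed against 600-700, 500-600, 400-500, 300-400 mL/day; 12 g ethanol per 100 mL wine; 11 items; range 0 to 55.

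**Step 1: the plan's own figure.** 11 items x 5 points = 55, which reproduces the stated maximum. The 5-point maximum is stated for the alcohol item and assumed for the other ten.

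**Step 2: pair the two lists in the order given.** The sentence says that the scores and bands correspond in order, so the first score goes with the first band.

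| Wine equivalent, mL/day | Ethanol, g/day | Points as written | Points with middle bands reversed | Written minus reversed |
|---|---|---|---|---|
| none | 0 | 0 | 0 | 0 |
| under 300 | under 36 | 5 | 5 | 0 |
| 300-400 | 36-48 | 1 | 4 | -3 |
| 400-500 | 48-60 | 2 | 3 | -1 |
| 500-600 | 60-72 | 3 | 2 | +1 |
| 600-700 | 72-84 | 4 | 1 | +3 |
| 700 | 84 | 0 | 0 | 0 |

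Ethanol = mL x 12/100; for example, 300 x 0.12 = 36 g.

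**Step 3: test the order among drinkers.** As written, the points run 5, 1, 2, 3, 4, 0: a drop of 4, a climb of 3, then a drop of 4. With the four middle scores reversed they run 5, 4, 3, 2, 1, 0, which agrees with both end points.

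**Step 4: size on the total score.** The largest error is 3 points: 3/55 = 5.5% of the range. In the two inner bands it is 1 point: 1/55 = 1.8%.

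**Step 5: can the questionnaire reach these bands?** The score is computed from the FFQ in Appendix 5.2. There a glass of wine is 125 mL, beer 240 mL and other alcohol 30 mL, and the top frequency is two or more times a day. The Protocol gives no numerical coding for that open-ended category.

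- Wine alone, coded at 2 a day: 2 x 125 = 250 mL/day, below every affected band.
- Wine alone, coded at 3 a day: 3 x 125 = 375 mL/day, inside the 300-400 band.
- Wine plus beer, both at 2 a day. Beer strength is not in the documents; I assume 4%, 5% or 6%, with an ethanol density of 0.789 g/mL. At 5%, beer adds 2 x 240 x 0.05 x 0.789 / 12 x 100 = 158 mL, giving 408 mL/day. Over the three strengths the total is 376 to 439 mL/day.
- All three drinks at 2 a day, with other alcohol assumed at 35% to 45%: 514 to 617 mL/day.

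Coded at 2 a day, then, the affected bands need top-category wine plus beer or spirits, and 600-700 mL/day is reached only at the stronger assumed strengths. A higher coding of the open category would bring more people in.

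**The case against.** The strongest reply is that this is a slip with little effect. The affected bands start at 36 g of ethanol a day, which few lactating mothers or milk donors are likely to report, and wine coded at 2 a day cannot reach them alone. The MedDietScore is not named in the Study II objectives (3.2), the sample size (3.3.5) or the statistical analysis (3.3.6). The one diet exposure that 3.3.6 specifies is macro- and micronutrient intake. The sentence is also written in the past tense and cites a published score, so an analyst working from that source may never use the wording here. All of this stands as a limit on the consequence. None of it removes the contradiction.

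Three stronger readings are tempting, and the documents do not support them.

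- **That the zero for abstainers is also an error.** An abstaining mother scores 5 points (5/55 = 9.1% of the range) below an otherwise identical mother who drinks anything under 300 mL/day. A reader might infer that the score is unsound in lactating women and should be re-run without alcohol. But the zero for no consumption is an explicit, uncontradicted rule of a cited score, and the documents give no abstention rate. Whether the score suits this population is a question about the instrument, not a mistake in the plan.
- **That every score above 300 mL/day is wrong.** At 700 mL/day the written and reversed rules both give 0. Above 700 mL/day the text gives no score at all, which is a separate gap.
- **That the main maternal diet exposure is compromised.** Section 3.3.6 refers generally to mothers' diet, which might include the score, but that is inference.

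**Conclusion.** The point holds for the band order alone. The contradiction can be shown from one sentence of section 3.3.3.1, without any outside source, and nothing elsewhere in the Protocol corrects it. Its size is at most 3 points on the 0-55 scale, confined to reported intake between 300 and 700 mL of wine equivalent a day, which is likely to be uncommon. No sample size, power figure or named endpoint changes.

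Two assumptions remain. The first is that the end points are right and the middle bands are transposed. That is the natural reading, because reversing four numbers restores a consistent scale, but the cited source should confirm it. The second is that few participants reach these bands, which depends on how the top FFQ category is coded. It is worth correcting because the rule is stated wrongly and the repair is trivial, not because the study's conclusions are at risk.

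**What to change.** In section 3.3.3.1, check the sentence against the scoring source it cites (reference 36 of the Study II list). Subject to that check:

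- give 4, 3, 2 and 1 points to 300-400, 400-500, 500-600 and 600-700 mL/day respectively;
- state whether the zero at 700 mL/day means 700 or more, so that higher intake has a score;
- while editing, say which band owns each shared boundary (400, 500 and 600 mL/day).

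The rule for no consumption stays as it is. Section 3.3.4.1 needs no edit because it refers back to this definition. The cost is one sentence and, if the score is already programmed, a check of that code. No new data are needed and the sample size is unaffected.

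### Study II records infant weight to the nearest 0.5 kg, too coarse for early weights and short-interval gain in infants born before 32 weeks

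*Protocol*

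**What the plan says.** Section 3.3.3.1 of the protocol (baseline phase, anthropometric assessment) has infant weight and recumbent length "measured on an electronic baby scale and on a neonatometer scale, to the nearest 0.5 kg and 0.5 cm respectively". Section 3.3.4.1 (observational phase) repeats the rule: "on an electronic baby scale and on a neonatometer scale, to the nearest 0.5 kg and 0.5 cm respectively". For the mothers, section 3.3.3.1 says: "Weight will be measured on a levelled platform scale to the nearest 0.5 kg". The protocol states no finer resolution for infants anywhere.

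The preterm groups are defined in section 3.3.2 by "Gestational age < 32 weeks for the group of preterm infants". Growth is objective (c) in section 3.2, weight is one of the dependent variables in section 3.3.6, and weight is named in the sample-size statement in section 3.3.5.

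Section 3.3.1 ends the baseline phase at complete enteral nutrition for preterm infants and at recovery of birth weight for full-term infants. On location, section 3.3.2 says: "Visits when full term infants recover of birth weight and at month 2 will be held at the participant's home". Sections 3.3.3.1 and 3.3.4.1 both have infant growth evaluated "by measuring weight, length and cranial perimeter upon every visit at the hospital".

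**The concern.** A half-kilogram step may serve for an adult, but it is a large fraction of the weight of an infant born before 32 weeks. The infant figure equals the maternal one in the same section and may have been carried over from it. Since it appears in both phases, it is the rule a site would follow.

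Study II asks whether milk composition relates to growth. If weights are stored on a 0.5 kg grid, most preterm infants share two or three recorded values early on, and gain over a week or two is mostly rounding. That information cannot be recovered afterwards. A weight-defined milestone for the full-term group also becomes unreliable if anyone reads it from the recorded weights.

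A second, smaller matter is that the recovery-of-birth-weight and month-2 visits take place at home, while the anthropometry text ties infant measurement to hospital visits.

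**Working it through.** **Inputs.** From the protocol: recording step w = 0.5 kg (3.3.3.1, 3.3.4.1), gestational age below 32 weeks (3.3.2), 25 dyads per group (3.3.5). The protocol gives no infant weights, SDs, weight losses or growth rates, so those below are assumptions shown as ranges. The 0.5 kg is a stated precision, so there is no calculation in the plan to reproduce.

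**Rounding error**, taken as uniform over one step:
- Maximum error = w/2 = 0.25 kg.
- SD of one reading = w/√12 = 0.5/3.464 = 0.144 kg.
- SD of a difference between two readings = w/√6 = 0.5/2.449 = 0.204 kg.

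**Early preterm weight (assumed).**
- At 1.0 kg: 0.25/1.0 = 25% of body weight. At 1.5 kg: 0.25/1.5 = 17%.
- With mean 1.2 kg and SD 0.30 kg, simulation puts 50% of infants at a recorded 1.0 kg and 40% at 1.5 kg, so about 90% share two values.

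**Short-interval preterm gain (assumed start 1.3 kg, SD 0.3 kg; gain 10-20 g/kg/day).** The chance that two recorded weights are equal is roughly 1 − gain/w.
- 7 days: mean true gain 0.094-0.194 kg, so 1 − 0.094/0.5 = 81% down to 1 − 0.194/0.5 = 61% show no recorded gain. Simulation agrees.
- 14 days: mean true gain 0.195-0.417 kg. Simulation gives 61% down to 19% with no recorded gain.
- Across these cases the SD of recorded gain is 0.20-0.24 kg, against a true SD of 0.02-0.09 kg.

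**Term infants around recovery of birth weight (assumed birth weight 3.3 kg, SD 0.45 kg; loss 5-10%).**
- Loss = 0.05 × 3.3 = 0.165 kg to 0.10 × 3.3 = 0.33 kg, below one step.
- Recorded nadir equals recorded birth weight in 1 − 0.165/0.5 = 67% down to 1 − 0.33/0.5 = 34%. Simulation agrees.

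**Effect on group comparisons.** Treating rounding as added noise, variance inflation is 1 + (w²/12)/SD² = 1 + 0.0208/SD².

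| True SD (kg, assumed) | Extra variance | Power at 25 per group |
|---|---|---|
| 0.2 | 52% | 83% |
| 0.3 | 23% | 90% |
| 0.5 | 8% | 93% |
| 0.8 | 3% | not computed |
| 1.0 | 2% | not computed |

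The power column is for a difference of 1.02 SD, which has 95% power without rounding: (1.960 + 1.645) × √(2/25) = 1.02. It is a yardstick for the loss, not the protocol's target of 0.10 SD.

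**With a finer step (illustrative).** At 5-10 g the maximum error is 0.0025-0.005 kg and the rounding SD 0.0014-0.0029 kg, 50 to 100 times smaller.

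**The case against.** Several points on the other side are sound and limit the finding.

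- **Not every growth association suffers.** Weight is an outcome in the section 3.3.6 growth models, so rounding mainly adds residual noise. At months 3 and 6, with an assumed SD of 0.8-1.0 kg, the cost is 2-3% of variance. The kilogram grid does not touch length, cranial perimeter or number of diseases.
- **The planned effect is not 10% of body weight.** Section 3.3.5 refers to a standardised difference, that is 0.10 SD. Nor does a group effect smaller than one step become undetectable, since means of rounded readings can differ by less than a step. Added variance is the right measure.
- **The baseline anchor does not collapse.** Recovery of birth weight applies only to the full-term group (25 of 75 dyads), and the protocol does not say it is judged from the rounded study weight. Even on the grid, 33-66% of the simulated term infants show a change.
- **The location wording does not prove that no weight is taken at home.** Section 3.3.1 allows observational-phase assessments in the hospital or at home, the design figure is not available, and the anthropometry text does not expressly exclude home weighing. Even so, section 3.3.4.1 refers to every visit or evaluation for several other assessments and limits only anthropometry to the hospital, so the texts need reconciling.
- **Operating procedures are deferred to WP3** (sections 3.3.3 and 3.3.4) and may specify finer weighing. That would conflict with the protocol's explicit 0.5 kg rather than cure it.

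None of this defends 0.5 kg for early preterm weights.

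**Conclusion.** The resolution is wrong as written. The rounding figures (0.25 kg maximum, SD 0.144 kg per reading and 0.204 kg per change) depend only on the stated step and uniform rounding. Their practical weight rests on assumed infant weights and growth, and the early harm is material across the ranges tried. It is concentrated in three places: early weights, short-interval gain in infants born before 32 weeks, and any use of recorded weight to identify recovery of birth weight in the full-term group. At later visits the loss is small.

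A reader might infer that all growth results of Study II are compromised, that recovery of birth weight cannot be established, or that no weight exists at that visit. The protocol supports none of these. A reader might also extend the complaint to the 0.5 cm step for length and cranial perimeter. No harm has been shown there, and no change is asked.

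**What to change.** - In sections 3.3.3.1 and 3.3.4.1, replace 0.5 kg for infants with the native resolution of the electronic baby scale, in grams (for example to the nearest 5-10 g), and align the text with the WP3 procedures.
- Reconcile the hospital-visit wording in those two sections with the home visits in section 3.3.2, so that it is clear infant weight is recorded at recovery of birth weight and at month 2.

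The first change is wording only, because the scale is already electronic. The second needs at most a portable scale at home visits that are already planned. Both should be made before infants are weighed, since rounded readings cannot be restored.
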